## 14 BUDGET

The budget for the DYNAMIC project administered from Rwanda is 1,799,200 Swiss francs (CHF), which is equivalent to approximately 7,150,000 Rwandan francs (FRw). **Table 8** breaks down the budget by project year (1st December 2019 through 31st December 2022) and project activity.

**Table 8:** Total budget in Swiss francs.

	Year 1	Year 2	Year 3	Total
Staffing	262'000	379'000	316'000	957'000
Training and workshops	42'500	27'500	12'500	82'500
IT infrastructure and equipment	45'750	5'000	3'000	53'750
Transportation	40'350	40'350	71'400	152'100
ePOCT+ implementation (Phases 1 and 2)	30'000	164'050	148'800	342'850
medAL-monitor/medAL-outbreak implementation	5'000	5'000	5'000	15'000
Mixed methods operational research	5'000	5'000	5'000	15'000
Stakeholder meetings and dissemination	45'000	40'000	36'000	121'000
Administrative costs	20'000	20'000	20'000	60'000
TOTAL				1'799'200

### ***Budget justification***

Staffing costs include salaries of all Swiss TPH local office in Kigali who are fully or partially allocated to the DYNAMIC project, as well as any temporary staff hired specifically for the project.

Training and workshop costs include rental fees for meeting venues, development and printing of all training materials, and per diems/allowances for meeting participants.

IT infrastructure and equipment costs include the procurement of all tablets, computers, servers, routers, and other items required to establish connectivity between tablets in study facilities and with the main server. This category also includes the set up and maintenance of the follow-up system via phone calls or automated SMS system.

Transportation costs include hiring or purchase and maintenance of vehicles, motorbikes, and other means of transportation between the study sites and/or to all the HFs for data collection or monitoring associated with all study activities. Driver salaries are also included in this category.

ePOCT+ implementation costs include the procurement of POC lab tests and medicines (if needed), printing of labels for identifying patients, salary top-ups for HF staff that perform additional duties for the study (if needed), internet bundles (if needed), and other miscellaneous expenses.

medAL-monitor/medAL-outbreak implementation costs include meetings and consultations with the users and relevant stakeholders regarding the content and visualization of the data, regular visits to district health officials to build capacity in interpreting the dashboards, and facilitating regular district visits to HFs for mentorship and supervision of the HWs.

Mixed methods operational research costs include the development of finalization of study tools, field data collection, software for data analysis, and the hiring of temporary field enumerators.

Stakeholder meetings and dissemination costs include rental fees for meeting venues, refreshments, development and printing of materials, reimbursement of transportation costs or per diems/allowances for meeting participants (if needed). Also included in this category are publication fees and development of dissemination materials at the end of the study (e.g. pamphlets, booklets, etc.).

Administrative costs include office space rental fees, office supplies, fees for various approvals, and other miscellaneous expenses.

## 16 APPENDICES

### Appendix A: Case Report Forms

- A1 – Information collected electronically during clinical consultations for the main study
- A2 – Information collected via a phone call or SMS or home visit for the main study

### Appendix B: Mixed-methods operational research tools

- B1 – Facility Assessment (adapted from SPA inventory tool)
- B2 – Quality of Care Consultation Observation Checklist (adapted from SPA sick child tool)
- B3 – Quality of Care Client Exit Interview (adapted from SPA sick child tool)
- B4 – Qualitative In-depth Interview: Health Worker
- B5 – Focus Group Discussion Guide: Health Worker
- B6 – Quantitative Survey: Health Worker
- B7 – Qualitative In-depth Interview: Caregiver
- B8 – Focus Group Discussion Guide: Caregiver
- B9 – Quantitative Survey: Caregiver
- B10 – Qualitative In-depth Interview: DHMT

### Appendix C: Informed Consents

- C1 – Participant information sheet and informed consent form for the main study
- C2 – Participant information sheet and informed consent form for the mixed-methods operational research studies
- C3 – Consent form for photo/video

### Appendix D: CVs of Team Members

### Appendix E: Example content of the algorithms

- E1 – Visual representation (diagrams) of the Tanzania algorithms
- E2 – Modifications made based on the Tanzanian clinical expert review

1.1 Hypothesis

In routine conditions, health workers (HWs) provided with an electronic clinical decision support algorithm (CDSA) on tablets or PCs can treat sick children attending primary health care facilities in Rwanda with appropriate antimicrobial prescriptions. More specifically, we hypothesize that with the use of CDSA called electronic point of care tests plus (ePOCT+) for case management of sick children in primary health care facilities, compared to routine care, less antibiotics will be prescribed at the initial consultation.

1.2 Objective

The overall objective of the DYNAMIC project is to improve the **integrated management of children with an acute illness** through the provision of an electronic CDSA (ePOCT+) to clinicians working at primary care level. The specific research objective of the Phase 1 of the DYNAMIC project is to determine if the use of ePOCT+ for case management of sick children in primary care, compared to routine care, results in less antibiotic prescriptions at initial consultation (primary outcome).

2. Study outcomes

2.1 Outcome definitions

2.1.1 Primary outcome

Percentage of children prescribed an antibiotic at initial consultation in the intervention group (ePOCT+) as compared to the control group (routine care)

Outcome measure: Prescription of oral or parenteral antibiotic at initial consultation, as reported by the HW.

Timing and method of measurement: Documented by the HW at the end of the initial consultation where the subject was enrolled (day 0).

Analysis type: Superiority

2.1.2 Secondary outcomes

All secondary outcomes are compared between the intervention (ePOCT+) and control (routine care) arms.

Percentage of children cured at day 7 in the intervention group (ePOCT+) as compared to the control group (routine care)

Outcome measure: The child is defined as being cured at day 7 if the caregiver says that the child is cured or has improved since the initial consultation. Non-referred secondary hospitalizations (if caregiver says that child was hospitalized between day 0 and day 7 but the electronic clinical data does not indicate a referral for hospitalization) will however be considered as clinical failures even if the child is already cured at day 7.

Timing and method of measurement: Assessment of subjective clinical cure by the caregiver, and history of non-referred hospitalization will be assessed by telephone or home visit follow-up 7 days (range 6-14 days) after enrollment of the subject. The day of enrollment of the subject is considered as day 0.

Analysis type: Superiority

Secondary consultations:

- % of children with one or more unscheduled re-attendance visits at any health facility by day 7

Timing and method of measurement: Telephone or home visit follow-up 7 days (range 6-14 days) after enrollment of the subject. The day of enrollment of the subject is considered as day 0.

Severe outcome by day 7:

- % of children with non-referred secondary hospitalization by day 7
- % of children who have died by day 7

Timing and method of measurement: Death and non-referred secondary hospitalization will be assessed by telephone or home visit follow-up 7 days (range 6-14 days) after enrollment of the subject. The day of enrollment of the subject is considered as day 0.

Primary referrals:

- % of children referred to hospital or inpatient ward at a health centre at initial consultation

Timing and method of measurement: Documented by the HW at the end of the initial consultation in the eCRF (control arm) or in ePOCT+ (intervention arm) when the subject was enrolled (day 0)

Appropriate case management for malaria at initial consultation

- % of febrile children tested for malaria by RDT and/or microscopy at day 0
- % of malaria positive children (positive RDT result OR positive microscopy result) prescribed an antimalarial at day 0
- % of malaria negative children prescribed an antimalarial at day 0
- % of untested children prescribed an antimalarial at day 0

Timing and method of measurement: Documented by the HW at the end of the initial consultation where the subject was enrolled (day 0)

Definitions:

Clinical cure is a positive answer to the question “Is the child cured?” or if not cured “Has the child improved?” asked to caregiver through a phone call at day 7. Non-referred secondary hospitalizations (see definition below) will be considered as clinical failures even if the child is already cured at day 7.

Clinical failure is a negative answer to the question “Is the child cured?” and “Has the child improved” asked to the caregiver through a phone call at day 7. Non-referred secondary hospitalization (see definition below) will be considered as a clinical failure even if the child is already cured at day 7.

Initial consultation is the first visit of a sick child for an acute problem at a HF participating in the study (and thus registered electronically); timeframe from completion of the initial visit up to midnight of the same day. The initial consultation is considered as day 0.

Re-attendance visit is a consultation (not necessarily at a HF participating in the study) taking place from the day after initial consultation up to day 14 included. A re-attendance visit can be scheduled (proposed by the HW on a certain day) or unscheduled (upon decision by caregivers).

Primary referral is a decision of referring or admitting the child at a hospital or health center for at least one night, taken by the HW at the initial consultation.

Secondary referral is a decision of referring or admitting the child at a hospital or health center taken by the HW during a re-attendance visit taking place from the day after initial consultation up to day 7 included.

Primary hospitalization is an admission to a hospital or health center ward for at least one night taking place the same day as the initial consultation

Secondary hospitalization is an admission to a hospital or health center ward for at least one night taking place from the day after initial consultation up to the phone call at day 7 included. A non-referred secondary hospitalization is a direct visit to hospital without a re-attendance visit the same day at a HF participating in the study. Non-referred secondary hospitalization will be determined if the caregiver reports during the day 7 phone follow-up that the child was hospitalized, even if there was no documentation of a referral from initial and re-attendance visits at participating health facilities.

Antibiotic prescription is any oral, intramuscular or intravenous (but not topical) antibiotic prescribed by a HCW during the initial consultation or a re-attendance visit.

Antimalarial prescription is any oral, rectal, intramuscular or intravenous antimalarial prescribed by a HCW during the initial consultation or a re-attendance visit.

Febrile child is a child with a history of fever (measured or suspected fever in the past 48 hours) or a high temperature.

Malaria testing is a malaria RDT or microscopy ordered by a HCW during an outpatient visit.

[figure not shown]
3. Methods

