Statistical considerations	
For the parallel cluster study in Phase 1, the primary analysis will evaluate whether the use of ePOCT+ for case management of sick children in PHC facilities results in decreased antibiotic prescriptions (superiority analysis) at the initial consultation. Superiority in antibiotic prescription is defined as a relative decrease of <math>\geq 25\%</math> in the proportion of children prescribed an antibiotic. We estimated a cluster size of 660 patients (monthly utilization of 220 – accounting for up to 30% non-adherence from 315 – over 3 months) and an intraclass correlation coefficient of 0.025. To have 80% power to detect a 25% reduction in antibiotic prescription (e.g. from 35% to 26%), for a one-sided hypothesis test at alpha of 0.025, we would require a minimum of 11 clusters per arm. With 16 clusters (or HFs) per arm, over 3 months, we expect a total of 10,500 participants per arm, this sample size is sufficient to test for non-inferiority in the secondary outcome (clinical cure at day 7) between the control and intervention groups.
 
We will test for significant difference in the primary outcome of antibiotic prescription between study arms by comparing proportions and their 95% confidence intervals. Primary analysis of superiority will be performed according to the intention-to-treat principle. The results will be stratified by sex, age group (young infants ages 1 to 59 days, children aged 2 months to 5 years, and children aged 5 to 14 years), and select clinical variables (respiratory symptoms, fever without clinical source, gastrointestinal complaints, skin problems, ear and throat problems, anemia, and malnutrition).
 
At the estimated utilization of the PHC facilities in Nyamasheke and Rusizi districts, we anticipate that approximately 150,000 consultations will be conducted using ePOCT+ throughout the study.

Study duration and schedule	
Pilot phase: April 2021 – August 2021
 
Phase 1 (data collection): September 2021 – April 2022
 
Phase 2 (data collection): June 2022 – December 2022
 
Implementation research (data collection): October 2020 – October 2022
 
Sustainability assessment: August 2022 – December 2022

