## 2 STUDY OBJECTIVES AND THEORY OF CHANGE

The **goal** of this study is to mitigate AMR using a novel dynamic ePOCT+ tool that helps front-line HWs manage sick patients, enhanced by additional digital platforms to promote uptake, sustainability, and integration of the tool into the health system. More specifically, this study seeks to:

### 2.1 Objective 1

**Improve the integrated management of children with an acute illness** (more specific and diverse diagnoses; reduced antibiotic prescriptions) through the provision of an electronic CDSA (ePOCT+) to clinicians working at primary care level.

*Hypothesis 1:* The use of ePOCT+ in the outpatient PHC setting in Rwanda will result in decreased prescription of antibiotics while maintaining similar clinical outcomes.

*Hypothesis 2:* The use of ePOCT+ in the outpatient PHC setting in Rwanda will result in improved quality of care.

### 2.2 Objective 2

**Improve the diagnostic and prognostic accuracy of the clinical algorithm across spatiotemporal variations in epidemiology and resources** through machine learning analyses of the data generated through the ePOCT+ tool, checked by clinical experts.

*Hypothesis 3:* Modifications in the electronic CDSA based on the results of ML analyses will enable similar or better outcomes over the course of the study despite temporal and spatial variability in disease patterns and/or availability of resources.

### 2.3 Objective 3

**Enhance the health management information system for monitoring and evaluation and supportive supervision** (increased number of meaningful indicators that are reviewed and actioned regularly) through additional data analysis and visualization of patient-level data generated by the ePOCT+ tool.

*Hypothesis 4:* The patient-level clinical data that is visualized and analyzed in near real-time will lead to improved ability of the DHMT to monitor the quality of patient care and undertake targeted supportive supervision of HFs and HWs.

*Hypothesis 5:* The patient-level clinical data that is visualized and analyzed in near real-time will lead to a more accurate epidemiological profile of the district and improved spatial and temporal resource allocation.

### 2.4 Objective 4

[figure not shown]
**Create a framework for the implementation of dynamic clinical decision support algorithms and supporting tools**, for large-scale, sustainable, and clinically responsible use of machine learning and data science in digital health.

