## 9 STATISTICAL METHODS

### 9.1 Sample size calculations

For the parallel cluster study in Phase 1, the primary analysis will evaluate whether the use of ePOCT+ for case management of sick children in PHC facilities results in decreased antibiotic prescriptions (superiority analysis) at the initial consultation. Superiority in antibiotic prescription is defined as a relative decrease of  $\geq 25\%$  in the proportion of children prescribed an antibiotic. We estimated a cluster size of 660 patients (monthly utilization of 220 – accounting for up to 30% non-adherence from 315 – over 3 months) and an intraclass correlation coefficient of 0.025. Non-adherence here is defined as HWs not using the application for all eligible patients that come to the HF for various reasons. To have 80% power to detect a 25% reduction in antibiotic prescription (e.g. from 35% to 26%), for a one-sided hypothesis test at alpha of 0.05, we would require a minimum of 11 clusters per arm. With 16 clusters (or HF) over 3 months, we expect a total of 10,500 participants per arm, this sample size is

sufficient to test for non-inferiority in the secondary outcome (clinical cure at day 7) between the control and intervention groups.

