## 9.2 Statistical analysis for the primary outcome measure in the parallel cluster study

Analyses will follow CONSORT guidelines (Schulz et al. 2010, Piaggio et al. 2012). A flowchart will describe the inclusion and follow-up of participants by study arm and by implementation block. Baseline characteristics and outcomes will be described by study arm and by implementation block using summary statistics such as median and interquartile range or number and percentage.

We will test for significant difference in the primary outcome of antibiotic prescription between study arms by comparing proportions and their 95% confidence intervals (CI). Primary analysis of superiority will be performed according to the intention-to-treat (ITT) principle (Committee for Proprietary Medicinal Products, 2001), with sensitivity analyses exploring differences between ITT, per-protocol and complete cases analysis approaches. The results will be stratified by sex, age group (young infants ages 1 to 59 days, children aged 2 months to 5 years, and children aged 5 to 14 years), and select clinical variables (respiratory symptoms, fever without clinical source, gastrointestinal complaints, skin problems, ear and throat problems, anemia, and malnutrition).

We will also use multi-level logistic regression with HF, patient ID, and time included as random effects (Kahan et al. 2012) to explore the effect of demographic and clinical variables on the outcome of interest. Effect modification by sex, age group, and the same clinical variables will be assessed by incorporating an interaction between arm and the respective variable, acknowledging that power will be low.

Primary analysis will be performed on initial consultations only (i.e. first visit for a particular illness episode), allowing multiple observations per patient over the course of Phase 1, but only one observation per illness. We will apply a 14-day period from the initial visit, during which no second initial visit will be possible and all subsequent visits will be marked as re-attendance by default. In the secondary sub-analyses, re-attendance visits between day 0 and day 7 will be considered, as well as longitudinal analyses of the complete visit history per patient. Further details on the primary and secondary analyses will be provided in the statistical analysis plan.

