## 9.5 Estimated number of beneficiaries

Throughout the study, we expect that an average of 212 children per month per HF will be managed using ePOCT+. In Phase 1, the number of direct beneficiaries include children attended to using ePOCT+ (n=24,000) and HWs using ePOCT+ (n=120) for a total of 24,120 people. Indirect beneficiaries may include caregivers and immediate family members who are less exposed to infectious diseases as a result of better cure rates of their child/sibling. Using an average rural household size of 4.3 people according to the 2012 Census, the number of expected indirect beneficiaries is approximately 151,368 (i.e. 3\*50,456, excluding the sick child who is a direct beneficiary). The actual number is likely to be lower due to the possibility of multiple visits per child over the course of Phase 1.

In Phase 2, we expect a maximum of around 48,000 consultations over 6-7 months. The number of direct beneficiaries will be less than this estimate, because children may come to the facility more than once, either for the same illness or a different illness over the course of the study. In Phase 2, approximately 200 HWs are expected to directly benefit from using ePOCT+ and their clinical decision support and e-learning functions. Additionally, approximately 10 users of medAL-monitor/medAL-outbreak at the district and national levels will also benefit directly. Lastly, all individuals who are

capacitated IT systems management, ML, adaptation of the algorithm through medAL-creator, etc. will be included as direct beneficiaries (n=50). Because of high coverage of the intervention in Phase 2, indirect beneficiaries will be the entire population of the intervention districts (n=783,000) as a result of 1) less exposure to infectious diseases due to better cure rates of sick children; 2) reduced drug pressure and likelihood of antibiotic resistance due to reduced antibiotic prescriptions; and 3) reduced risk of illness due to more effective outbreak detection and response.

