#### *Community:*

Communities in the intervention area are also expected to benefit from the project in several ways. Reduced antibiotic prescriptions will reduce antimicrobial drug pressure in the community, and hence the risk of drug resistance. Better cure rates are expected to lessen the exposure to infectious diseases in the community.

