3.2 Allocation of health facilities to study arms

The 32 health facilities to be included in the study will be selected from all eligible health facilities in the participating districts (Rusizi and Nyamasheke). Eligible health facilities include public health centers with at least 19 consultations with children between 2 months and 5 years of age per week. Cluster inclusion and exclusion criteria will first be applied to the full list of health facilities in the participating districts prior to selection of the 32 health facilities. Health facilities (or clusters) will be allocated (1:1), to using ePOCT+ (intervention) or routine care (control group). Due to the pragmatic nature of the study, randomization is not possible. Health facilities will be allocated first to one of the three implementation blocks using geographical considerations, and then split into study arms, also using geographical considerations. Similar sample size by study arm and by implementation group will be maintained as much as possible.

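### The SAP labels day-7 cure a superiority analysis, while the protocol speaks of non-inferiority and similar outcomes; nothing reconciles them, and no margin or ICC for cure is given

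*SAP*

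**What the plan says.** **SAP 2.1.2** lists cure at day 7 first among the secondary outcomes and gives it "Analysis type: Superiority". The same label stands under the primary outcome in 2.1.1, where it is not in question.

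**Protocol 9.1**, at the end of the sample-size paragraph, says that about 10,500 children per arm are "sufficient to test for non-inferiority in the secondary outcome (clinical cure at day 7) between the control and intervention groups". The synopsis carries the same statement.

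**Protocol 2.1, Hypothesis 1**, says that use of ePOCT+ "will result in decreased prescription of antibiotics while maintaining similar clinical outcomes".

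**Protocol 9.2** passes the detail on: "Further details on the primary and secondary analyses will be provided in the statistical analysis plan".

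**SAP 3.3** repeats the protocol's sample-size text without the non-inferiority sentence and does not comment on the omission. **SAP 6.1** analyses binary secondary outcomes by random-effects logistic regression, with odds ratios and two-sided 95% confidence intervals, and describes outcomes by arm. It also chooses a complete-case analysis for cure and calls it the most conservative option, because counting children lost to follow-up as not cured would shrink the difference between arms.

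**The concern.** The two documents put different questions to the same outcome. Superiority asks whether cure is better with ePOCT+. Non-inferiority asks whether cure is not worse by more than a stated amount. Hypothesis 1 is of the second kind: fewer antibiotics at no cost in cure.

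The choice affects what can be concluded. If cure is truly equal and there is no confounding, a two-sided 5% superiority test is non-significant 95% of the time and favours ePOCT+ about 2.5% of the time. That non-significant result does not show that cure was maintained. The confidence interval for the odds ratio will bound the loss of cure, but no rule set in advance says how large a loss would be acceptable. If someone then wishes to claim maintained cure, the tolerable loss could be chosen after the interval is known.

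Cure is the only Phase 1 secondary outcome measure named in protocol 7.1, and it is the clinical counterpart to prescribing less.

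**Working it through.** **1. The plan's own figure.** Inputs from SAP 3.3: 35% against 26%, 80% power, two-sided 0.05, cluster size 660, ICC 0.025.

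- n per arm before clustering = [1.960·√(2·0.305·0.695) + 0.842·√(0.35·0.65 + 0.26·0.74)]² / 0.09² = 410 after rounding up.
- Design effect = 1 + 659·0.025 = 17.475.
- Clusters = 410·17.475/660 = 10.86, so 11. This matches the plan.
- 16·660 = 10,560, which agrees with the stated 10,500.

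The adequacy statement for cure cannot be reproduced in this way, because it has no margin and no ICC for cure.

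**2. What the same sample gives for cure.** Inputs:

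- 97% cure in both arms (SAP 6.1 expects 3% not cured).
- 16 clusters of 660 per arm. SAP 3.3 describes 660 as already net of non-adherence and/or loss to follow-up.
- Cure ICC: 0.025 is borrowed from the antibiotic outcome; 0.01, 0.005 and 0.001 are assumptions.

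Formulas:

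- Effective n per arm = 10,560 / (1 + 659·ICC).
- SE of the difference under equal cure = √(2·0.97·0.03 / effective n).
- Smallest non-inferiority margin with 80% power at one-sided 0.025 = (1.960 + 0.842)·SE.
- Superiority power = Φ(d/SE₁ − 1.960), with SE₁ = √[(p₁(1−p₁) + p₂(1−p₂)) / effective n].

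| Cure ICC | 0.025 | 0.01 | 0.005 | 0.001 |
|---|---|---|---|---|
| Design effect | 17.475 | 7.59 | 4.295 | 1.659 |
| Effective n per arm | 604 | 1,391 | 2,459 | 6,365 |
| SE, equal cure (points) | 0.981 | 0.647 | 0.487 | 0.302 |
| Smallest margin, 80% power (points) | 2.75 | 1.81 | 1.36 | 0.85 |
| Superiority power, 97% to 98% | 20% | 39% | 61% | 95% |
| Superiority power, 95% to 98% | 81% | 99% | >99% | >99% |

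The 97% to 98% gain is an assumption. The 95% to 98% gain is the one that protocol 1.5 reports for ePOCT against routine care in Tanzania.

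Protocol 9.1 attributes the reduction to 660 to non-adherence alone, so day-7 loss might come on top. Removing a further 25% (the top of the 13–25% range in SAP 6.1) leaves 495 per cluster and margins of 2.77, 1.85, 1.41 and 0.93 points, which is little different.

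**3. The complete-case rationale.** If a share L is lost equally in both arms and counted as not cured, each cure proportion is multiplied by 1 − L, and so is the difference. For L = 13–25% the factor is 0.87 to 0.75. Shrinking the difference makes superiority harder to show and brings a loss of cure closer to zero. With roughly equal loss, avoiding the shrinkage is therefore the cautious choice for non-inferiority and not for superiority, which is the test that the SAP names.

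**The case against.** The best reply is that superiority is deliberate and that the SAP governs. Much of this stands.

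- The protocol sentence states what the sample could do. It does not plan a non-inferiority test, and 9.2 leaves the analyses to the SAP. A reader might infer that the SAP breaks a planned non-inferiority test; the documents do not go that far.
- The protocol (synopsis and section 4) and SAP 3.1 call the study a superiority trial, although superiority is given a definition only for antibiotic prescription.
- Better cure is anticipated: "Better cure rates are expected to lessen the exposure to infectious diseases in the community", and families are described as "less exposed to infectious diseases as a result of better cure rates of their child/sibling". Protocol 7.1 says that ePOCT gave similar or possibly better outcomes.
- The SAP's hypothesis and objective concern antibiotics only, and SAP 3.3 drops the non-inferiority sentence.
- Superiority is a workable test for a gain like the 95% to 98% precedent. Whether that gain carries over to Rwanda is unknown.

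A reader might also infer that the sample is too small for cure. The documents do not support that. Protocol 4.1 pools all groups for cure to obtain enough children, and the sample may be ample or not, depending on the margin and the ICC. Nor is it right that nothing in the plan bears on Hypothesis 1: the by-arm summaries and the odds ratios with intervals do.

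The reply does not remove the conflict. If superiority is intended, the protocol sentence is out of date, and the part of Hypothesis 1 on similar outcomes has no decision rule.

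**Conclusion.** The inconsistency is real and should be fixed. Three statements on the same outcome point in two directions, no text reconciles them, and the adequacy claim rests on a margin and an ICC that are not given. Under the stated assumptions the claim holds for margins above about 2.75 points at ICC 0.025, and above about 0.85 points at ICC 0.001. The documents do not say where in that range the study lies, or whether such margins would be acceptable.

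These figures assume no confounding. SAP 3.2 says "Due to the pragmatic nature of the study, randomization is not possible", so residual differences between arms may affect any comparison of cure. Their size cannot be derived from the documents.

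The point concerns a secondary outcome. The primary analysis and the success criterion in SAP 6.1 are not affected.

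**What to change.** Reconcile SAP 2.1.2 with the protocol synopsis, protocol 9.1 and Hypothesis 1 by one of two routes, and say which is intended.

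**(a) Non-inferiority.**
- Label cure as non-inferiority, with a margin on a stated scale (risk difference or odds ratio), justified by the sponsor and fixed before outcome data are seen.
- Assess it by the two-sided 95% confidence interval, and test superiority afterwards if non-inferiority holds.
- In the synopsis and 9.1, replace the adequacy statement with the power for that margin over a stated range of cure ICCs.
- The direction of the complete-case argument in SAP 6.1 then fits, given roughly equal loss in both arms.

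**(b) Superiority.**
- Keep the SAP label and delete the non-inferiority statement from the synopsis and 9.1.
- Report the risk difference with its confidence interval beside the odds ratio.
- State that a non-significant result will not be read as maintained cure.
- Correct the complete-case rationale in SAP 6.1, since with roughly equal loss avoiding dilution is not conservative for superiority.

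The cost is wording and at most one extra estimate. Under (a) the sponsor commits to a margin and to a power figure that may be less favourable than the present text suggests. Under (b) the study gives up a formal claim of maintained cure.
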